**Trial Protocol** 

will be performed at all visits

marrow and CT scan may be performed at the discretion of the investigator. Results should be reported in case these examinations have been performed within 4 weeks prior to screening.

A patient enrolled in a cohort during dose escalation may receive up to 4 courses of BI 836826. In patients who unequivocally show clinical benefit from the drug, the administration of 4 additional treatment courses may be possible in agreement between the investigator and the Clinical Monitor at Boehringer Ingelheim. Provided that the administration of 4 courses is considered safe, up to 8 courses may be administered for patients enrolled in the expansion cohort.

Each patient will be closely monitored for infusion-related reactions and tumour lysis syndrome.

Safety

during the treatment phase.

Disease status will be assessed every two weeks until the EOT visit, including physical examination, clinical assessment of CLL and blood samples. At the discretion of the investigator (i.e., if medically indicated), a CT scan and a bone marrow examination may be performed to confirm a CR 8 weeks after a patient for the first time meets the criteria of a CR. Results of any CT scan or bone marrow examination performed during the conduct of the trial should be reported in the eCRF.

During the follow-up phase, disease status evaluations (physical examination, clinical assessment of CLL, and blood samples) should be performed at least every 4 weeks for 6 months after the EOT visit. More frequent visits may be indicated, e.g. for follow-up of laboratory parameters or adverse events which have not been resolved at the EOT visit.

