5.1.2.4.1 Complete remission (CR)

CR requires all of the following criteria for a period of at least 2 months:

- A1 Peripheral blood lymphocytes (evaluated by WBC and differential count) below  $4 \times 10^9$ /L.
- A2 Absence of significant lymphadenopathy, i.e. no lymph nodes > 1.5 cm.
- A3 No hepatomegaly.
- A4 No splenomegaly.
- A5 Bone marrow aspirate and biopsy demonstrate absence of residual disease.
- B1 Platelets more than  $100 \times 10^9$ /L (without exogenous growth factors or transfusion).
- B2 Hemoglobin more than 110 g/L (without exogenous growth factors or transfusions)
- B3 Neutrophils more than  $1.5 \times 10^9$ /L (without exogenous growth factors).
- C Absence of disease-related constitutional symptoms.
- 4.

Group A criteria define the tumor load, group B criteria define the function of the hematopoietic system. In case all criteria A and C are met, but a patient has a persistent anemia or thrombocytopenia or neutropenia apparently unrelated to CLL, but related to drug toxicity, the patient should be categorized as CR with incomplete marrow recovery (CRi).

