#### 5.1.2.4.3 Partial remission (PR)

To define a PR, at least 2 criteria of category A and 1 criterion of category B have to be met for a period of at least 2 months.

- A1 Decrease in the number of blood lymphocytes by 50% or more compared to the pretreatment value.
- A2 Reduction in lymphadenopathy by 50% or more, defined as a decrease in lymph node size by 50% or more, either in the sum products of up to 6 lymph nodes or in the largest diameter of the enlarged lymph nodes detected prior to therapy, AND no increase in any lymph node, and no new enlarged lymph node. In small lymph nodes

(<2cm) an increase of less than 25% is not considered to be significant.

- A3 Decrease in hepatomegaly by 50% or more
- A4 Decrease in splenomegaly by 50% or more.
- A5 Reduction by 50% or more in bone marrow infiltration, or B-lymphoid nodules.
- B1 Platelets more than  $100 \ge 10^9$ /L or 50% improvement over baseline (without exogenous growth factors or transfusion).
- B2 Hemoglobin more than 110 g/L or 50% improvement over baseline (without exogenous growth factors or transfusions).
- B3 Neutrophils more than  $1.5 \ge 10^9$ /L or 50% improvement over baseline (without exogenous growth factors).
- 5.1.2.4.4 Progressive disease (PD)

At least one of the following criteria is required:

- A1 An increase in the number of blood lymphocytes by 50% or more over baseline with an absolute number of B-lymphocytes of at least  $5 \times 10^9$ /L.
- A2 Progression of lymphadenopathy, defined as appearance of any new lymph node > 1.5 cm or an increase by 50% or more in the greatest determined diameter of any previous site, or appearance of a new organ infiltrate other then hepatomegaly or splenomegaly.
- A3 An increase in the previously noted enlargement of the liver by 50% or more or new appearance of hepatomegaly.
- A4 An increase in the previously noted enlargement of the spleen by 50% or more or new appearance of splenomegaly.
- B1 Decrease of platelet counts by more than 50% or to less than  $100 \times 10^9$ /L secondary to CLL and unrelated to autoimmune cytopenia
- B2 Decrease of hemoglobin levels by more than 20 g/L or to less than 100 g/L secondary to CLL and unrelated to autoimmune cytopenia
- T Transformation to a more aggressive histology, e.g. Richter syndrome.

During therapy, cytopenia cannot be used to define disease progression. The progression of any cytopenia unrelated to autoimmune cytopenia as defined by criteria B1 and B2 which

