#### 7.3.2.5 Best overall response

Best overall response is the best response (CR, PR, SD or PD in this order) with respect to all time points. Remission rate is the rate of patients that either have CR or PR as best overall response. Best overall response and remission rate will be analysed descriptively. Frequency distributions and other descriptive statistical measures will be used to examine these variables.

These time-to-event variables will be analysed descriptively or with the Kaplan-Meier method if applicable. Details of censoring rules will be provided in the statistical analysis plan.

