5.2.2 Other Secondary endpoints

Note: For the response/efficacy analyses with respect to overall response assessment by investigator used: If patients would have their examinations contributing to the disease assessment over a number of days, the earliest date of the multiple examinations should be considered.

For the response/efficacy analyses with respect to lymphocytes and blood counts only laboratory data assessed >= 8 days after the last infusion and with reported laboratory response assessment on-treatment and before start of new Chronic Lymphocytic Leukaemia (CLL) therapy is used. The reason for this approach is that otherwise the respective values of lymphocytes and blood counts would be biased due to the infusion after which an immediate change in values of the respective blood parameters is observed. This change though does not reflect an efficacy effect.

Number of lymphocytes in the peripheral blood

The secondary endpoint with respect to number of lymphocytes in the peripheral blood is defined as "Best % change from baseline in number of lymphocytes in the peripheral blood".

Blood counts (haemoglobin, platelets, neutrophils)

The secondary endpoints with respect to blood counts are defined as

- "Number of patients with improved haemoglobin count for at least two subsequent response assessments"
- "Number of patients with improved platelet count for at least two subsequent response assessments"
- "Number of patients with improved neutrophil count for at least two subsequent response assessments"

An improvement is indicated by the fulfilment of the criteria for "Complete Remission" or "Partial Remission", i.e.

- Haemoglobin count: Greater than 11g/dL or increase of 50% or more compared to baseline if haemoglobin is less than or equal to 11g/dL
- Platelet count: Greater than 100 000/ μ L or increase of 50% or more compared to baseline if platelets are less than or equal to 100 000/ μ L
- Neutrophil count: Greater than 1500/ μL or increase of more than 50% compared to baseline if neutrophil count is less than or equal to $1500/\mu L$

Best overall response:

Response will be assessed according to the NCIWG guidelines (R10-4429) based on laboratory data from the peripheral blood and clinical examination by the investigator. Each patient will be assigned to one of the following categories:

- complete remission (CR)
- complete remission with incomplete marrow recovery (CRi)
- partial remission (PR)
- stable disease (SD)

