- progressive disease (PD)
- not evaluable (NE)

Best overall response (CR, CRi, PR, SD, PD or NE in this order) is defined as the best overall response obtained since the start of study treatment until PD or start of next CLL therapy. Post-treatment assessments will be considered for the evaluation of best overall response as long as no further CLL therapy has started.

Progression free survival (PFS):

PFS is defined as the time from first treatment with BI 836826 until disease progression or death, whichever occurs first. A patient has an evaluable response assessment if either CR, CRi, PR, SD or PD has been assigned by the investigator.

Derivation of PFS is defined as PFS [days] = date of outcome – date of first administration of BI 836826 + 1.

The censoring rules and the applicable dates of outcome for PFS are given following table.

Table 5.2.2: 1 Derivation rules for progression-free survival

Situation	Outcome (event or censored)	Date of outcome
Disease progression or death	Event	Date of first disease progression or death
No disease progression or death without additional CLL therapy	Censored	Date of last response assessment
No disease progression or death with additional CLL therapy	Censored	Date of last response assessment before start of new CLL therapy
No baseline or post-baseline disease assessment and without death	Censored	Date of first administration of BI 836826
No baseline or post-baseline disease assessment and death on or before second planned disease assessment (i.e. 28 days after first administration of BI 836826)	Event	Date of death
No baseline or post-baseline disease assessment and death after second planned disease assessment (i.e. 28 days after first administration of BI 836826)	Censored	Date of first administration of BI 836826

Failure free survival (FFS):

FFS is defined as the time from first administration of BI 836826 until disease progression or death or start of next CLL therapy.

[figure not shown]
Derivation of FFS is defined as FFS [days] = date of outcome – date of first administration of BI 836826 + 1.

[figure not shown]
The censoring rules and the applicable dates of outcome for FFS are given in following table.

Table 5.2.2: 2 Derivation rules for failure-free survival

Situation	Outcome (event or censored)	Date of outcome
Disease progression or death or start of next CLL therapy	Event	Date of first disease progression or death or start of next CLL therapy

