Best overall response will be analysed descriptively. Frequency distributions will be used to examine this endpoint. The number of patients that have either CR, CRi or PR as best overall response will be tabulated separately (to determine the remission rate).

Progression-free and Failure-free survival

PFS and FFS will be analysed exploratory using Kaplan-Meier methods for all patients of the Treated Set.

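### Best overall response in the SAP carries no persistence condition, although the protocol requires CR and PR to last at least 2 months, so a response seen at one visit can count as a remission

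*SAP*

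**What the plan says.** Protocol 5.1.2.4.1 states: "CR requires all of the following criteria for a period of at least 2 months". Under protocol 5.1.2.4.3, PR needs at least two group A criteria and one group B criterion, and these "have to be met for a period of at least 2 months". Protocol 5.1.2.4 has response assessed after each course, at end of treatment (EOT) and at every follow-up visit.

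The analysis sections do not carry the duration forward. Protocol 7.3.2.5: "Best overall response is the best response (CR, PR, SD or PD in this order) with respect to all time points". In SAP 5.2.2, best overall response is "defined as the best overall response obtained since the start of study treatment until PD or start of next CLL therapy", and post-treatment assessments count until further CLL therapy starts. SAP 7.5.2: "The number of patients that have either CR, CRi or PR as best overall response will be tabulated separately", which gives the remission rate.

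For categories and criteria, SAP 5.2.2 relies on the investigator's assessment and on the same published guideline that the protocol cites. The SAP text available for review gives no minimum duration, no confirming visit and no rule for a CR or PR that is not sustained.

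**The concern.** The protocol defines a remission as a state that lasts. The SAP derives it as the best category reached over repeated assessments. A patient who meets the PR criteria at one visit and has lost them by the next fails the protocol's definition but can still enter the numerator of the remission rate.

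The SAP does use persistence elsewhere. Improved haemoglobin, platelet or neutrophil counts must be seen at two subsequent response assessments, with thresholds taken from the remission criteria. Overall response, the more consequential summary, has no such safeguard.

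At stake is how the activity data are read cohort by cohort. Protocol 2.2 lists clinical response parameters among the inputs that could support an optimal biological dose if no MTD is reached.

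**Working it through.** **1. The plan's own figure.** The documents state no expected remission rate and no power for response. The only planned number that bears on it is the denominator. Protocol 7.6 assumes 3 cohorts of 1, 3 of 3 and 3 of 6: 3×1 + 3×3 + 3×6 = 30. Adding up to 30 expansion patients gives 60, as stated.

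**2. Length of 2 months.** SAP section 7 converts days to months as days × 12/365.25, so 2 months = 2 × 365.25/12 = 60.9 days. Protocol 3.2 places the optional CT and marrow check of a CR at 8 weeks = 56 days. The two lengths differ.

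**3. Nominal assessment calendar.** Inputs are 14-day courses, EOT 14 days after the last dose, and follow-up every 28 days for about 6 months (six visits). Visit windows and delays are ignored.

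| | 4 courses | 8 courses |
|---|---|---|
| Last dose | 1 + 14×3 = day 43 | 1 + 14×7 = day 99 |
| EOT | day 57 | day 113 |
| Response assessments to EOT | 15, 29, 43, 57 | 15, 29, 43, 57, 71, 85, 99, 113 |
| Follow-up | 85, 113, 141, 169, 197, 225 | 141, 169, 197, 225, 253, 281 |
| Longest span to EOT | 57 − 15 = 42 days | 113 − 15 = 98 days |

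**4. What a 2-month condition would require (60.9 days).**
- With 4 courses, no response can be shown to last 2 months by EOT, because 42 < 60.9. A response first seen on day 15 is first verifiable on day 85 (70 days).
- With 8 courses, only responses first seen on days 15, 29 or 43 can be verified by EOT, since 113 − 60.9 = 52.1. A day 15 response is again first verifiable on day 85, because 71 − 15 = 56 falls short.
- The definition matters. With 4 courses, a response seen from day 29 to day 85 spans exactly 56 days. It passes at 8 weeks and fails at 60.9 days.
- With 4 courses, a response first seen on day 169, 197 or 225 cannot be verified in planned follow-up, because 225 − 169 = 56 < 60.9.

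Under the SAP wording none of this is checked. A CR or PR entered on day 15 counts with no later assessment.

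**5. Size.** SAP section 7 presents efficacy by dose cohort, and protocol 3.1 gives three to six patients per cohort once single-patient cohorts end. One unsustained PR adds:
- cohort of 3: 1/3 = 33 percentage points
- cohort of 6: 1/6 = 17 points
- expansion cohort of 12 to 30: 1/12 = 8 to 1/30 = 3 points

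For the overall rate, the share s of apparent responders who do not persist is not in the documents. As an assumption range, the sustained rate is r × (1 − s):

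| Apparent rate r | s = 10% | s = 25% | s = 50% |
|---|---|---|---|
| 20% | 18% | 15% | 10% |
| 40% | 36% | 30% | 20% |

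**The case against.** The best defence is that duration is already part of the category. The SAP presumes familiarity with the protocol and tabulates what the investigator assigns. If investigators enter CR or PR only after 2 months, the SAP need not derive duration again. This is possible, but neither document says it. It also sits awkwardly with categories assigned at each assessment and with the 42-day span above: in a 4-course patient, no CR or PR could then be entered by EOT.

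The SAP also follows protocol 7.3.2.5, which has no duration clause. That stands. The gap lies within the protocol as well as between the two documents, so both texts need alignment.

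Three stronger readings are tempting, and the documents do not support them:

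- **Protocol 3.2 proves that responses are recorded on first sight.** It allows CT and marrow examination "to confirm a CR 8 weeks after a patient for the first time meets the criteria of a CR". Meeting the criteria is not the same as being entered as a CR, the check is discretionary, and it says nothing about PR.
- **Infusion effects on blood values will produce false PRs.** On the usual schedule, response is assessed about 13 to 14 days after an infusion, outside the period under 8 days that the SAP excludes for blood values. PR also needs two group A criteria, so a lymphocyte fall alone is not enough. An EOT assessment brought forward when a patient stops mid-course is a narrow exception.
- **Repeated looks multiply the rate.** With 15% durable responders and a 2%, 5% or 10% chance of a transient PR at each of 10 visits, 0.15 + 0.85 × [1 − (1 − p)^10] gives 31%, 49% or 70%. None of these inputs comes from the documents. Node and spleen findings in one patient are not independent between visits, and PD or new therapy shortens the window.

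**Conclusion.** The point holds as a gap in the derivation. The protocol requires 2 months' persistence for CR and PR. SAP 5.2.2 and 7.5.2, and protocol 7.3.2.5, define best overall response and the remission rate without it, so a response seen at one visit can count. That reading rests on two things: assessments are made visit by visit, and no rule tells investigators to withhold CR or PR until 2 months have passed.

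The documents do not show that the rate will be inflated, or by how much. What follows from them is the leverage of one patient: 33 points in a cohort of 3 and 17 in a cohort of 6. The endpoint is secondary, no formal tests are planned, there are no key secondary endpoints, and the MTD and DLT analyses are untouched. The change is worth making before the response tables are produced, but it does not bear on the trial's primary conclusion.

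**What to change.** In SAP 5.2.2 and 7.5.2, with protocol 7.3.2.5 brought into line:

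1. Count a patient as a responder (CR, CRi or PR) only if response of at least that category is maintained at assessments spanning at least 2 months.
2. Define 2 months once, reconciling the 8 weeks in protocol 3.2 with the 60.9 days from the SAP's conversion.
3. Let a CR that is not sustained, but stays at PR or better throughout, count as PR. A CR–PR–CR sequence should not fall to SD.
4. Put responses whose persistence cannot be verified (new therapy, telephone follow-up, early end of follow-up) in a separate unconfirmed category. Forcing them to SD would bias the rate downward.
5. State which criteria must be seen again, because marrow examination is discretionary.
6. Tabulate confirmed and unconfirmed remission rates side by side, by dose cohort.

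First establish how the eCRF captures response. If sites already withhold CR or PR until 2 months have passed, the SAP should say so, and the derivation must not impose the duration a second time.

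The cost is some programming on assessments already scheduled, plus a review of unverifiable cases. The headline rate may fall, and some responses will stay unconfirmed, particularly those first seen late in follow-up.

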5.1.2.5 Progression free survival (PFS)

PFS is defined as the time from first treatment with BI 836826 until disease progression or death.

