No disease progression, death or new CLL therapy	Censored	Date of last response assessment
No baseline or post-baseline disease assessment and without death or new CLL therapy	Censored	Date of first administration of BI 836826
No baseline or post-baseline disease assessment and death on or before second planned disease assessment (i.e. 28 days after first administration of BI 836826)	Event	Date of death
No baseline or post-baseline disease assessment and death after second planned disease assessment (i.e. 28 days after first administration of BI 836826)	Censored	Date of first administration of BI 836826

[figure not shown]

Proprietary confidential information © 2016 Boehringer Ingelheim International GmbH or one or more of its affiliated companies

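### PFS and FFS derivation tables: an unassessed death after day 28 fits both an event row and a censoring row, and PFS censoring at new CLL therapy depends on what is recorded later

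*SAP*

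**What the plan says.** Protocol 7.3.2.5 leaves the censoring rules to the SAP, so the two tables in SAP 5.2.2 govern.

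- **Definitions.** The SAP states that "PFS is defined as the time from first treatment with BI 836826 until disease progression or death, whichever occurs first". Protocol 5.1.2.5 likewise states that "PFS is defined as the time from first treatment with BI 836826 until disease progression or death". For FFS the SAP states that "FFS is defined as the time from first administration of BI 836826 until disease progression or death or start of next CLL therapy". None of these makes an exception for patients without assessments.
- **PFS, Table 5.2.2:1.** Row 1 makes progression or death an event, with no condition on assessments or new therapy. Row 3, "No disease progression or death with additional CLL therapy", censors at the last response assessment before the new therapy. Rows 4 to 6 deal with unassessed patients: alive (censored at first administration); "No baseline or post-baseline disease assessment and death on or before second planned disease assessment" (event at death); and "No baseline or post-baseline disease assessment and death after second planned disease assessment" (censored at first administration).
- **FFS, Table 5.2.2:2.** Row 1 is an event, dated "Date of first disease progression or death or start of next CLL therapy". Row 3 censors at first administration only under the condition "No baseline or post-baseline disease assessment and without death or new CLL therapy". The two death rows repeat those of the PFS table and do not mention new therapy.

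Neither table says in what order the rows apply or which one prevails.

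**The concern.** There are two separate problems.

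1. **Overlap, both tables.** An unassessed patient who dies after day 28 (28 days after first administration) satisfies row 1 and the last row, which give opposite outcomes. Two programmers could derive different results for the same patient. If the last row prevails as an exception, a known death is left out, contrary to the bare definitions. In FFS, a new-therapy failure that has already happened can be left out as well.

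2. **Outcome-dependent censoring, PFS only.** Rows 1 and 3 do not overlap. But of two patients who start new CLL therapy on the same day, the one with a later recorded progression or death is an event at that later date, and the other is censored before the therapy. Whether a patient is censored there depends on what is recorded afterwards.

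At stake are the reported PFS and FFS estimates (PFS alone for the second problem). The MTD does not depend on them.

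**Working it through.** **The plan's own figures.** Two 14-day courses give 2 × 14 = 28 days, matching the stated second planned assessment. The planned size also reproduces: 3×1 + 3×3 + 3×6 = 30, plus up to 30 in expansion, gives 60.

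**Part 1: reading each row literally.** "Unassessed" cases below are patients with neither a baseline nor a post-baseline assessment. If the rows mean that either one is missing, more patients overlap.

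| Unassessed patient | Row 1 | Specific row |
|---|---|---|
| PFS: dies 59 days after first dose | Event, 59 + 1 = 60 days | Last row: censored, 0 + 1 = 1 day |
| FFS: new therapy day 20, alive | Event, day 20 | None (row 3 requires no new therapy) |
| FFS: new therapy day 20, dies day 60 | Event, day 20 | Last row: censored at first administration |
| FFS: new therapy day 20, dies day 25 | Event, day 20 | Early-death row: event, day 25 |

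Lines 2 and 3 of the table show the substantive error: under the exception reading, dying on day 60 cancels a failure on day 20. Line 4 is a conflict of dates only.

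**Part 1: size.** Suppose half of a group is event-free at six months when the unassessed death is counted, with no other censoring. Removing that one failure gives 30/59 = 50.8% for 60 patients, 15/29 = 51.7% for 30, and 3/5 = 60.0% for 6. SAP 7 presents efficacy by dose cohort, so the last case is relevant.

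The documents give no rate for unassessed patients. Assume 2% to 5%, exponential survival with median 180 to 365 days, and deaths between day 28 and day 196 (14 days plus about six months, 14 + 182). The expected number among 60 is 60 × rate × [exp(−28 ln2/m) − exp(−196 ln2/m)], where m is the median:

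- lowest: 60 × 0.02 × 0.259 = 0.3
- highest: 60 × 0.05 × 0.428 = 1.3

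With missingness at random and median PFS 150 days, simulated 6-month PFS is on average 0.1 to 0.5 point higher under the last row than with the deaths counted (0.4 to 0.9 at median survival 90 days).

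**Part 2: size.** Assumed: median PFS 150 days, 20% to 40% starting new therapy before progression, median survival after it 180 to 365 days, progression hazard after it unchanged or halved, assessments every 28 days, 280-day horizon. Average difference in 6-month PFS, present rule minus censoring everyone before new therapy:

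| Later events captured | Difference (points) |
|---|---|
| None | 0 |
| Half of deaths | −0.4 to −2.4 |
| All deaths | −0.7 to −4.1 |
| All deaths and progressions | −1.4 to −6.9 |

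The last line is unlikely once visits have ended. Against following everyone through new therapy, with later progression not captured, the difference runs from +4.7 (no deaths captured, hazard unchanged) to −3.8 (all deaths captured, hazard halved).

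**Direction in a single data set.** Take six patients: events on days 100 and 120, and three event-free past day 183.

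- *Part 1.* The sixth is unassessed and dies on day 250. With the death counted, day-183 PFS is 5/6 × 4/5 = 4/6 = 66.7%. Under the last row it is 4/5 × 3/4 = 3/5 = 60.0%.
- *Part 2.* The sixth is last assessed on day 56, starts new therapy on day 60 and dies on day 250. The present rule gives 66.7%; censoring at day 56 gives 60.0%.

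Both results run opposite to the simulated averages. Early censoring removes a patient who was still event-free at day 183 from the risk set.

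**The case against.** **The last row is an exception, so nothing is ambiguous.** This is probably the intent. If row 1 prevailed, the early-death row would be redundant and the last row could never apply. Censoring rules also commonly qualify a bare definition. What remains is that the SAP does not say so, and that the exception gives the wrong FFS result when new therapy has already started.

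**The group is close to empty.** Largely right. Protocol 6.2.1 lists a disease assessment at screening, and 5.1.2.4 has response assessed after each course, at EOT and in follow-up. Protocol 6.2.3.1 asks for the EOT information at once when a patient stops mid-course. The 2% to 5% rate has no basis in the documents.

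**The PFS new-therapy rule is a matter of preference, and FFS covers these patients.** Partly right. Protocol 5.1.2.6 adds FFS precisely for patients who start another therapy without formal progression. Visits end at new therapy (6.2.3.2), so little may be recorded afterwards, and with nothing recorded the rule equals censoring everyone. But Table 5.2.2.2:1 asks for deaths to be reported to the end of follow-up, so some will be. FFS does not repair PFS, which is reported in its own right.

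**Stronger readings that fail.** A reader might infer that the last row always raises PFS and FFS, or that the present new-therapy rule always gives lower PFS than censoring everyone. The six-patient examples refute both for PFS, and the first example carries over to FFS if nobody starts new therapy.

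**Conclusion.** Both defects stand on the text, and both are minor.

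- **Overlap.** Tables 5.2.2:1 and 5.2.2:2 give two outcomes for an unassessed death after day 28, without precedence. The likely intended reading departs from the definitions, and in FFS it discards a new-therapy failure because the patient later died.
- **New therapy.** PFS censoring at new CLL therapy depends on the later recorded outcome.

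Under the assumed inputs, the average effect on 6-month PFS is below one point for the overlap. For new therapy it is between zero and a few points, depending on how many later events are captured. A single patient matters mainly in a small dose cohort. Every rate behind these figures is an assumption, and the direction is not guaranteed in either part.

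It would be tempting to conclude that the tables favour the drug, or that the trial's conclusions are at risk. The documents support neither: SAP 7.5.2 makes PFS and FFS exploratory, Protocol 7.2 excludes formal tests, and the MTD rests on DLTs.

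**What to change.** **FFS.** For every patient, whatever the assessments, count the first of progression, death or start of new CLL therapy as the event at its date. Limit censoring of unassessed patients to those with none of the three. The two death rows then fall away.

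**PFS.** State row precedence. Count a death without prior new CLL therapy as an event at its date, and keep the day-28 censoring as a sensitivity analysis. For patients who start new CLL therapy without prior progression or death, apply one rule whatever is recorded later: censor at the last response assessment before the therapy (at first administration if there is none). Keep as events the deaths on or before day 28 in unassessed patients, as the early-death row now does. Without this exception, an unassessed patient with new therapy on day 20 and death on day 25, now an event under both matching rows, would be censored at first administration. Report an analysis that counts captured later deaths as a sensitivity analysis.

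**Cost.** Revised table wording and a small derivation change, with no new data. Estimates may move slightly in either direction. Censoring at new therapy may itself be informative, which the second sensitivity analysis addresses. The early-death exception leaves a small outcome dependence, and an unassessed patient who starts new therapy and dies after day 28 stays censored at first administration in the primary PFS analysis. FFS counts that patient.
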